### **9.1 STUDY DESIGN**

This is a meta-analysis of 3 studies (1245.25, 1245.110, and 1245.121), which are randomised, placebo-controlled, double-blind, parallel-group, and event-driven studies. A meta-analysis of the 3 studies is considered appropriate to explore the risk for LLA events due to the large study size (approx. 14 000 patients in total in the 3 studies) and long-term exposure (median treatment exposure was 2.6 years in 1245.25; treatment exposure of up to 3 years are expected in ongoing studies 1245.110 and 1245.121). Data from individual patients from the 3 studies, not the result estimates of the 3 studies, will be pooled in the meta-analysis.

[figure not shown]
Study 1245.25 has been completed and the CTR is available [[c02695839](#)]. The study title is “A Phase III, multicentre, international, randomised, parallel group, double blind cardiovascular safety study of BI 10773 (10 mg and 25 mg administered orally once daily) compared to usual care in type 2 diabetes mellitus patients with increased cardiovascular risk”.

Study 1245.110 and 1245.121 are ongoing and the CTPs are available [[c03946327](#), [c09098452](#)]. The study title of 1245.110 is “A phase III randomised, double-blind trial to evaluate efficacy and safety of once daily empagliflozin 10 mg compared to placebo, in patients with chronic heart failure with preserved ejection fraction”. The study title of 1245.121 is “A phase III randomised, double-blind trial to evaluate efficacy and safety of once daily empagliflozin 10 mg compared to placebo, in patients with chronic heart failure with reduced ejection fraction”.

The overall designs of the studies are shown in [Figure 9.1: 1](#).

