## **9.9 LIMITATIONS OF THE RESEARCH METHODS**

This will be a meta-analysis of 3 studies with heterogeneous patient populations. Patients with type 2 diabetes mellitus and increased cardiovascular risk (1245.25) will be pooled together with patients with chronic heart failure with preserved (1245.110) or reduced (1245.121) ejection fraction (see [Section 9.2.2](#) for more detailed eligibility criteria) in SAF-M1. In general, some heterogeneity between the studies can be expected due to the different populations involved in the trials to be pooled. The degree of heterogeneity of the treatment effect between studies will be assessed statistically and clinically/visually. For time-to-event outcomes, visual inspection of heterogeneity includes a forest plot of the individual study hazard ratios, alongside the corresponding estimate from the individual patient data meta-analysis in SAF-M1 and SAF-M2. For statistical assessment of heterogeneity, a Cox model will be provided including in addition the treatment-by-study interaction term. The p-value of

the interaction term from the Cox model in SAF-M1 and SAF-M2 will be used as a statistical measure for heterogeneity. For binary outcomes (frequencies and incidence rates of LLAs and AEs related to amputation), visual inspection of heterogeneity will be performed using forest plots. These will display the frequencies/incidence rates per treatment arm within each study, alongside the corresponding estimate from the pooled analysis in SAF-M1 and SAF-M2. For statistical assessment of heterogeneity,  $I^2$  will be calculated for the relative risk of an LLA or AEs related to amputation. If heterogeneity between studies is present, potential sources of variability will be assessed clinically and conclusions outlined in the final report.

The Cox model is based on the proportional hazards assumption. The proportional hazards assumption will be explored by plotting  $\log(-\log(\text{survival function}))$  against the  $\log$  of time by treatment group and checked for parallelism. The interaction of treatment with  $\log$  of time will be included in the model described above for an exploratory analysis. Further, Schoenfeld residuals for each covariate and treatment will be plotted against time and  $\log(\text{time})$ . If the proportional hazards assumption cannot be verified, potential sources will be assessed clinically and conclusions outlined in the final report.

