4.3 PLANNED ANALYSES

The following sections describe in detail the statistical analyses planned for disposition, demographic, and baseline characteristics considerations as well as the analyses planned for the safety endpoints described in [Section 4.1](#).

Meta-analysis methods

The meta-analysis will be performed in an exploratory manner. For the main outcomes (time to first LLA and time to first AE related to amputation), a Cox proportional hazards regression model for modelling the time to first event will be used, including the factors study, DM status (T1DM, T2DM, no diabetes) and treatment (all empa vs placebo). Study is assumed as a fixed effect in this meta-analysis.

Frequency analyses

For frequency analyses based on pooled data the estimates for the relative frequency is defined as follows:

$$\hat{p}_j = \frac{\sum_{i=1}^k w_{ji} \cdot \hat{p}_{ji}}{\sum_{i=1}^k w_{ji}}, \text{ where}$$

p_{ji} relative frequency in treatment group j and study (i=1,.., k)

$$w_{ji} = \frac{n_{ji}}{\sum_i n_{ji}}$$

denotes the weight of study i , $i=1, \dots, k$ in treatment group j

n_{ji} number of patients in treatment group j and study i ($i=1, \dots, k$)

Incidence rates

The frequency (%) of AEs does not take into account the duration of treatment. This is particularly important when studies with different treatment durations are pooled for analysis. In this case incidence rates may provide more accurate comparisons among groups.

Incidence rate is the number of new cases of an event occurring in a specified time period divided by the cumulative time at risk. The derivation of time at risk and incidence rates is as follows:

Patients with event:

time at risk in days = date of start of first event – treatment start date + 1

Patients without event:

time at risk in days = last date on treatment + 7 days*(or last date in study for secondary analysis based on ITT approach) – treatment start date + 1

* This is according to the definition of the residual effect period of 7 days as defined in the trial protocols for safety analyses for treatment emergent events.

The incidence rate per 100 patient years can then be calculated as follows:

Incidence rate [1/100 pt-yrs] = 100 * number of patients with event / sum of time at risk over all patients [years].

The estimate for a pooled incidence rate in treatment group j is defined as follows:

$$\widehat{IR}_j = \frac{\sum_{i=1}^k w_{ji} \cdot \widehat{IR}_{ji}}{\sum_{i=1}^k w_{ji}}, \text{ where}$$

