\widehat{IR}_{ji} Incidence rate in treatment group j and study ($i=1, \dots, k$)

$$w_{ji} = \frac{t_{ji}}{\sum_i t_{ji}}$$

denotes the weight of study i , $i=1, \dots, k$ in treatment group j

$w_{ji} = \frac{t_{ji}}{\sum_i t_{ji}}$ denotes the weight of study i , $i=1, \dots, k$ in treatment group j

t_{ji} sum of time at risk in treatment group j and study i ($i=1, \dots, k$)

The incidence rates will be calculated with two types of time at risk calculations.

The main analysis is the on-treatment approach where patients are censored at the date of treatment stop + 7 days and the secondary analysis is the ITT analysis where patients are censored at the last day of follow-up if no event occurred.

Time to event analyses

Kaplan Meier (KM) methods of cumulative incidence functions will be performed for time to event data (time to first event).

For pooled data across studies the cumulative incidence functions will be shown overall and stratified by study. The main analysis will be performed with censoring at the date of last study medication intake + 7 days for patients without event. An additional analysis will be performed whereby patients with no events will be censored at the date of last follow-up.

Cox proportional hazards models for modelling time to first event will be applied using factors study, DM status (T1DM, T2DM, no diabetes) and treatment (all empa vs placebo). For treatment comparison, hazard ratios with corresponding 95% confidence intervals as well as corresponding p-values will be presented.

The proportional hazards assumption will be explored by plotting $\log(-\log(\text{survival function}))$ against the log of time by treatment group and checked for parallelism. The interaction of treatment with log of time will be included in the model described above for an exploratory analysis. Further, Schoenfeld residuals for each covariate and treatment will be plotted against time and $\log(\text{time})$.

Competing risk analyses for time to event endpoints

Death is a competing risk for lower limb amputations. A competing risk analysis using a regression model by Fine and Gray (1999) [1] for amputations considering death as a competing event will therefore be performed. The regression model will include the following co-variables: study, diabetes mellitus (T1DM, T2DM, no diabetes), and treatment (empa vs. placebo).

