In addition as graphical display a cumulative incidence analysis for amputations and competing event of death will be performed.

The competing risk analysis will be performed according to the standard time to event analysis with censoring at the date of last study medication + 7 days and as additional secondary analysis censored at the date of last follow up.

Trial heterogeneity

In general, some heterogeneity between the studies can be expected due to the different populations involved in the trials to be pooled.

The degree of heterogeneity of the treatment effect between studies will be assessed statistically and clinically/visually.

For time-to-event outcomes, visual inspection of heterogeneity includes a forest plot of the individual study hazard ratios, alongside the corresponding estimate from the individual patient data meta-analysis in SAF-M1 and SAF-M2. For statistical assessment of heterogeneity, a Cox model will be provided including in addition the treatment-by-study interaction term. The p-value of the interaction term from the Cox model in SAF-M1 and SAF-M2 will be used as a statistical measure for heterogeneity.

For binary outcomes (frequencies and incidence rates of LLAs and AEs related to amputation), visual inspection of heterogeneity will be performed using forest plots. These will display the frequencies/incidence rates per treatment arm within each study, alongside the corresponding estimate from the pooled analysis in SAF-M1 and SAF-M2. For statistical assessment of heterogeneity, I^2 will be calculated for the relative risk of an LLA or AEs related to amputation.

If heterogeneity between studies is present, potential sources of variability will be assessed clinically and conclusions outlined in the final report.

Sensitivity analysis for missing dates

For LLA a sensitivity analysis will be conducted for incidence rate calculation in SAF-M1 and SAF-M2 excluding all patients with amputations with missing onset dates. This analysis will only be performed if >10% of onset dates are missing.

Overview of performed analyses

Due to the different study designs not all analyses will be performed for each of the 2 pools. The following table indicates which safety analyses will be performed for which pool and the individually studies.

Table 4.3: 1

Overview of analyses that will be performed for the different study poolings and for the individual study

	Poolings and individual study

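### Treatment × log(time) and treatment × study are each tested alone in the pooled Cox model, so with unequal follow-up each test can partly pick up the other's effect (minor; mainly the secondary outcome)

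*SAP*

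**What the plan says.** The base model in SAP 4.3 has main effects only: "Cox proportional hazards models for modelling time to first event will be applied using factors study, DM status (T1DM, T2DM, no diabetes) and treatment". Study enters as a factor ("Study is assumed as a fixed effect in this meta-analysis"), and the model is not described as stratified by study.

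Two diagnostics extend this model separately:

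- **Proportional hazards.** "The interaction of treatment with log of time will be included in the model described above for an exploratory analysis". At that point in the SAP, the only Cox model already described is the main-effects one. A log(-log) plot by treatment group and Schoenfeld residual plots accompany it.
- **Heterogeneity.** Later in the same section, "a Cox model will be provided including in addition the treatment-by-study interaction term". Its result is given a role: "The p-value of the interaction term from the Cox model in SAF-M1 and SAF-M2 will be used as a statistical measure for heterogeneity".

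On duration, protocol 9.1 states that "median treatment exposure was 2.6 years in 1245.25" and that "treatment exposure of up to 3 years are expected in ongoing studies 1245.110 and 1245.121". SAP 4.3 itself gives differing treatment durations as a reason for using incidence rates. If proportional hazards fails, protocol 9.9 says: "If the proportional hazards assumption cannot be verified, potential sources will be assessed clinically and conclusions outlined in the final report".

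**The concern.** The study main effect adjusts for different baseline hazards, but not for a treatment effect that differs by trial. When the trials leave the risk set at different times, two situations become hard to tell apart:

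- a constant HR that differs between 1245.25 and the heart failure trials makes the pooled HR drift as the trial mix changes, so the time test can fire;
- a common HR that changes with time is averaged over different spans in each trial, so the study test can fire.

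The first is a population difference (T2DM with cardiovascular risk against heart failure). The second is an early or late drug effect. The report is meant to trace such signals to their source, and the two sources mean different things for safety.

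**Working it through.** **1. The plan's own figures.** 2345 + 2342 + 2333 = 7020, and 7020 + 4126 + 2850 = 13,996, which matches the stated total of about 14,000. Allocation in 1245.25 is (2345 + 2342) : 2333 = 4687 : 2333 = 2.01 : 1. The heart failure trials have (4126 + 2850)/2 = 3488 per arm. The plan states no event target, power or test level for either interaction, so the rest needs assumptions (two-sided 0.05 throughout).

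**2. Follow-up.** Protocol section 6 gives these windows from start to end of data collection:

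- 1245.25: 26 August 2010 to 21 April 2015 = 4.65 years
- 1245.110: 4 April 2017 to Q3 2021 = 4.24–4.49 years
- 1245.121: 21 June 2017 to Q3 2020 = 3.03–3.28 years

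These are upper limits for any one patient. For 1245.110 the window is longer than the 3 years in protocol 9.1.

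**3. Mechanism by hand.** Suppose HR = 1.0 in 1245.25 and 1.97 in heart failure (1.97 is the canagliflozin figure in protocol section 7), with equal placebo rates λ. A trial's information is roughly events × p(1−p), where p is the empagliflozin share of events.

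- 1245.25: 7020λ × 0.668 × 0.332 ≈ 1558λ
- Heart failure: 3488λ × 2.97 × 0.663 × 0.337 ≈ 2313λ

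The heart failure weight at the start is 2313/(1558 + 2313) = 0.60, so the pooled HR is about 1.97^0.60 = 1.50. It goes to 1.00 once only 1245.25 remains, although no trial's HR has changed.

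**4. Simulation, Cox partial likelihood.** Arm sizes come from the protocol. Assumptions: placebo rates 0.65/0.50/0.40 per 100 patient-years in 1245.25/1245.110/1245.121, then ×5 and ×15 for more frequent events; 8% discontinuation per year; follow-up of 1.2–4.65 years in 1245.25 (median 2.5), and 0.3–3.0 or 0.5–3.5 years in the heart failure trials (medians about 1.5–1.8); diabetes status omitted. Likelihood-ratio tests; 1500, 1000 and 400 runs. The Monte Carlo standard error at 5% is √(0.05 × 0.95/n) = 0.6, 0.7 and 1.1 points. Each cell gives the false rejection rate, alone → with both terms in the model.

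| Events | Time test; HR 1.0 in 1245.25, 2.0 in heart failure | Study test; common HR(t) = t^0.5 |
|---|---|---|
| about 175–200 (LLA-like) | 7.5–7.6% → 5.5–6.3% | 7.1–10.2% → 5.1–5.3% |
| about 840–950 (×5) | 12.9–17.9% → 4.3–6.0% | 16.5–24.2% → 4.4–4.8% |
| about 2400–2600 (×15) | 23.3% → 4.8% | 37.2% → 4.8% |

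With milder effects (HR 1.5, or t^0.25) the LLA-like rates are 5.1–6.5%. With no effect at all, both tests reject in 4–7%. With equal follow-up in all trials, the false test stays at 3–6%, so unequal follow-up is the cause. Power for the genuine interaction falls by at most 2.6 points when the other term is added (for example 0.520 to 0.511).

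**5. Frequent secondary outcome.** Assumed rate 8 per 100 patient-years, heart failure follow-up to 3 years. With HR 1.0 against 1.97, the time test rejects in 41–52% across runs. With a common HR stepping to 1.97 after year 2, the study test rejects in 33–46%. With both terms the rates are about 4–12.5%; a step is not linear in log(time), so that term does not absorb it fully. With 1245.110 followed to 4.3 years, 41% becomes 17% and 34% becomes 18%. LLA-like rates across these runs are about 4–10%.

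**6. Pooled log(-log) plot.** Assume no effect in any trial and LLA rates of 0.8 (1245.25) and 0.3 (heart failure).

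- Early empagliflozin rate: (4687 × 0.8 + 3488 × 0.3)/8175 = 0.587
- Early placebo rate: (2333 × 0.8 + 3488 × 0.3)/5821 = 0.500

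The crude ratio is 1.17 early and 1.00 once only 1245.25 remains, so the pooled curves are not parallel even under the null.

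**The case against.** A reader might infer that the final report would name the wrong cause. The documents do not support that. In the frequent-outcome runs where the artefact is large, the true source was significant in 98–100% of runs and had the smaller p-value in at least 98%. With HR 1.0 against 1.97, for instance, the median treatment × study p-value was about 4 × 10⁻¹⁴. At LLA-like counts the true source is less conspicuous (power about 0.5 for treatment × study at HR 1.0 against 2.0), but there the false signal barely exceeds 5%.

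A reader might also infer that late risk sets come only from 1245.25. The section 6 window for 1245.110, the larger heart failure trial, leaves that open.

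Much is already planned. Cox and time-to-onset analyses are specified for each trial, forest plots show the study HRs, and SAF-M2 leaves out 1245.25. Within one trial, a time check cannot be confounded by treatment × study, and protocol 9.1 runs analyses per study unless otherwise indicated. In protocol 9.9 the log(time) sentence comes after the treatment × study model, so a joint model is a possible reading there. Both checks are exploratory and carry no decision rule.

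Most of this stands and limits the severity. What remains: the SAP puts the log(time) sentence first, so the joint reading is not available there; no proportional-hazards check is listed explicitly by study; and a forest plot cannot show whether differing HRs reflect differing follow-up.

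**Conclusion.** The point holds as a minor one about interpreting exploratory diagnostics. It does not alter the primary HR. For LLA the effect is negligible to small, about 4–10% rejection against 5%. For the secondary outcome it can be material, roughly 15–50%, if events occur at about 8 per 100 patient-years and HRs are near 2. The lower end applies if 1245.110 runs for about 4.2–4.5 years, the upper end if it stops near 3. The documents give no event rates and no median follow-up for the heart failure trials, so these sizes rest on the assumptions shown; the mechanism and its direction do not.

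**What to change.** In SAP 4.3 and protocol 9.9, state that for SAF-M1 and SAF-M2:

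- the treatment × log(time) check is also fitted with treatment × study in the same model, and each interaction is reported with and without the other;
- the log(-log) and Schoenfeld plots are drawn within each study.

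Using the same wording in both documents also removes the ambiguity in protocol 9.9. The cost is a short text change, a few extra model runs and a very small loss of power for each interaction test. Confidence intervals for the interactions, and a treatment × study test with truncated follow-up, are optional extras.

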## **9.5 STUDY SIZE**

This meta-analysis will be based on patients treated with at least 1 dose of study medication (“treated set”) in the 3 studies. Patients are assigned to treatment groups according to randomisation.

Study 1245.25 included 7020 patients treated with empagliflozin 10 mg (N = 2345), empagliflozin 25 mg (N = 2342), or placebo (N = 2333).

Study 1245.110 will randomise approx. 4126 patients to empagliflozin 10 mg or placebo in a 1:1 ratio. Study 1245.121 will randomise approx. 2850 patients to empagliflozin 10 mg or placebo in a 1:1 ratio. Almost all randomised patients are expected to be treated.

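### In SAF-M1, with study as a Cox factor and unequal allocation across trials, the treatment-by-log(time) check can mistake different trial hazard shapes for a time-varying treatment effect

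*SAP*

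**What the plan says.** SAP section 4.3 (time to event analyses) specifies that the Cox models "will be applied using factors study, DM status (T1DM, T2DM, no diabetes) and treatment (all empa vs placebo"), and under meta-analysis methods adds: "Study is assumed as a fixed effect in this meta-analysis". Protocol 9.7 and 9.7.1 agree. Study is therefore a covariate and not a stratum; only the Kaplan-Meier curves are stratified by study.

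The proportional-hazards check uses the same model: "The interaction of treatment with log of time will be included in the model described above for an exploratory analysis". It is accompanied by log(-log) plots by treatment group and by Schoenfeld residual plots for treatment and for the other model terms, study included. No significance level is attached to any of these. On a failed check, Protocol 9.9 says: "If the proportional hazards assumption cannot be verified, potential sources will be assessed clinically and conclusions outlined in the final report". No stratified refit is named.

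Protocol 9.5 gives the allocation in the completed trial: "Study 1245.25 included 7020 patients treated with empagliflozin 10 mg (N = 2345), empagliflozin 25 mg (N = 2342), or placebo (N = 2333"). The two heart failure trials are planned at about 4126 (1245.110) and 2850 (1245.121) patients, each split equally between the 10 mg dose and placebo.

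**The concern.** A study factor lets the three trials differ in the level of their hazard but forces the ratio of those hazards to be constant over time. If the diabetes trial's hazard falls while the heart failure trials' hazards rise, or the reverse, the model gets the share of events coming from 1245.25 wrong in one direction early and in the other direction late. Because 1245.25 has a larger empagliflozin share than the other two trials, that misfit is correlated with treatment, and the correlation changes sign over time. A treatment-by-log(time) term is built to detect exactly that pattern.

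What is at stake is the reading of a diagnostic. A signal caused by differences between trials could receive a clinical explanation in the report as an effect of empagliflozin that changes with time. A real change could also be diluted, which matters in a safety evaluation.

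**Working it through.** **Sizes and allocation (Protocol 9.5).**
- 2345 + 2342 + 2333 = 7020, and 7020 + 4126 + 2850 = 13 996. This reproduces the plan's figure of about 14 000 patients.
- All-empagliflozin share: 4687/7020 = 0.668 in 1245.25, and 0.50 in 1245.110 and 1245.121.
- SAF-M1 totals: empagliflozin 4687 + 2063 + 1425 = 8175; placebo 2333 + 2063 + 1425 = 5821. So 4687/8175 = 57% of empagliflozin patients but 2333/5821 = 40% of placebo patients come from 1245.25.

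**Mechanism.** Take no treatment effect and the same censoring in both arms of each trial. Let π*(t) be the true probability that an event at time t comes from 1245.25, and π(t) the probability under the factor model. The expected misfit in the treatment score at each event is

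(π*(t) − π(t)) × (0.668 − 0.500) = 0.168 × (π*(t) − π(t)).

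The score equation for study makes π* − π sum to about zero over the events, so the main treatment effect is not shifted. Weighted by log(t), the sum is generally not zero, so the interaction is shifted. With equal allocation the multiplier is zero and the effect disappears.

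**Simulation.** From the documents: trial sizes, allocation, model terms, and follow-up ("median treatment exposure was 2.6 years in 1245.25; treatment exposure of up to 3 years are expected in ongoing studies 1245.110 and 1245.121"). Assumed: Weibull shapes, event counts, the censoring pattern, 50% diabetes and no T1DM in the heart failure trials, and a two-sided 5% Wald test. The true HR is 1 throughout the table; 500 to 3,000 replicates per row. At 500 replicates the Monte Carlo standard error at 37% is √(0.37 × 0.63/500) = 2.2 points.

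| Outcome, mean events | Shape 1245.25 / HF trials | Study as factor | Study as stratum |
|---|---|---|---|
| LLA, 171 | 1.0 / 1.0 | 5.3% | 5.1% |
| LLA, 161 | 0.8 / 1.2 | 5.6% | 5.1% |
| LLA, 183 | 1.2 / 0.8 | 5.8% | 4.8% |
| LLA, 156 | 0.7 / 1.3 | 6.5% | 3.8% |
| LLA, 311 | 0.7 / 1.3 | 10.9% | 5.5% |
| LLA, 148 | 0.5 / 1.5 | 11.9% | 4.4% |
| LLA, 205 | 1.5 / 0.5 | 12.4% | 4.7% |
| Related AEs, 2901 | 1.0 / 1.0 | 3.5% | 4.0% |
| Related AEs, 2834 | 0.9 / 1.1 | 12.4% | 5.2% |
| Related AEs, 2765 | 0.8 / 1.2 | 36.3% | 4.7% |
| Related AEs, 3055 | 1.2 / 0.8 | 37.4% | 4.6% |
| Related AEs, 1342 | 0.8 / 1.2 | 16.6% | 4.5% |
| Related AEs, 2706 | 0.7 / 1.3 | 65.2% | 5.3% |

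A separate simulation at about 1,900–2,000 related-AE events gave 11% (1.0/0.8), 13% (0.9/1.1) and 27% (1.2/0.8), against 5–6% stratified.

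**Control.** With 1245.25 set to 1:1 and the shapes still different, the factor model gives 4.3% for LLA (0.5/1.5) and 4.3% for related AEs (0.7/1.3). Unequal allocation is therefore a necessary part of the cause.

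**Size of the spurious term.** It is about 0.03–0.10 per unit of log(time). At 0.053 (shapes 1.2/0.8), moving from 3 months to 3 years, log(12) = 2.485, multiplies the apparent HR by exp(0.053 × 2.485) = 1.14.

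**Masking.** With shapes 1.2/0.8, about 2,000–2,160 events and a true coefficient of −0.12 (400 replicates), power is 91% stratified and 43% with study as a factor. The mean estimates are −0.126 and −0.069.

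**Main HR.** Without the interaction, the factor model averages 0.995–1.004 when the truth is 1, 1.497 when it is 1.5, and 1.303 when it is 1.3.

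**The case against.** The case for leaving the plan alone is substantial.

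- Nothing in the documents shows that the hazard shapes differ. SAP 4.3 expects some heterogeneity between trials but says nothing about shape over time. A reader might infer that the check will raise a false alarm; the documents support only that it can. This stands.
- The check is exploratory and has no threshold, so a false-rejection rate rests on a 5% rule that the plan does not state. This stands. The rate still measures how misleading the term can be.
- A reader might infer that the pooled HR, or the LLA result, is compromised. It is not: the HR is unbiased, and for LLA the inflation is slight unless the shapes differ strongly or events are more numerous.
- Other planned outputs would help expose the artefact. With a score test against log(time) standing in for the Schoenfeld plots (200 replicates, about 2,150–2,220 related-AE events), study signalled in every replicate. Its median absolute z was 5.4–12.0, against 0.9–2.0 for treatment. At about 150 LLA events study signalled in 31–90%. The single-trial analyses are free of this mechanism. This stands in part: these outputs point to the source, but they do not correct the contaminated term, and no refit is planned.
- The subgroup Cox models and the Fine-Gray model also include study. The plan attaches no treatment-by-log(time) check to them, so this point does not require changing them.

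**Conclusion.** The point holds as a conditional weakness of one diagnostic in SAF-M1. Study as a factor combined with about 2:1 against 1:1 allocation lets differences in hazard shape between trials load on treatment-by-log(time), in either direction. For AEs related to amputation the false-signal rate is about 11–37% at about 2,000–3,300 events with moderate shape differences, lower with fewer events and higher with larger differences. For LLA it is about 6–12%, the upper end needing strong shape differences or about 300 events. All these rates rest on assumed shapes, event counts and censoring.

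It does not follow that a false signal is expected, that the treatment HR is wrong, or that SAF-M2 or the single trials share the problem: allocation is 1:1 in both SAF-M2 trials, and a single trial has only one allocation ratio. The change is still worth making because it removes a bias that the design makes possible, at almost no cost.

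**What to change.** In SAF-M1, stratify the Cox model by study (STRATA study), keeping diabetes status and treatment as covariates. Run treatment-by-log(time) and the treatment Schoenfeld plots in that stratified model, and draw the log(-log) plots by treatment within each study. The treatment-by-study heterogeneity model can stay, because that interaction remains estimable with study as a stratum. Using the same form in SAF-M2 is optional, for consistency. Period-specific hazard ratios are not required.

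The cost is one model statement and matching wording in SAP 4.3 and Protocol 9.7, 9.7.1 and 9.9. No precision is lost: the simulated standard error of the log HR was the same either way (0.0438 for related AEs, 0.1622 for LLA). The only thing given up is a hazard ratio between studies, which is not an objective in Protocol section 8.
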